9.4 DATA SOURCES

The study will use the Military Health Systems (MHS) database.

The US DoD operates the largest cradle-to-grave health care database in the US. The military database has over 30 billion archived records, including 5 billion online records spanning

over 11 years for EMRs, 20 years of ePrescribing, and decades of prescription, inpatient, and outpatient data. Its size increases by 230,000 outpatient encounters and 2,700 inpatient admissions every day. As a single-payer, fully budgeted \$55 billion health care system, there are uniform medical coverage and pharmacy benefits for the 10 million active people served. The pharmacy benefit in particular has minimal expenses for most patients, thus positioning the DOD as a dynamic platform for patient adherence. It is completely free of expense for patients utilizing military treatment facilities (MTF) and clinics. These data are commercially available only through [REDACTED].

The MHS provides 2 types of care to its beneficiaries. It provides direct care through a network of over 60 military hospitals and 411 clinics and purchased care provided by civilian providers financed through managed care contracts and fee-for-service reimbursements globally. Direct care accounts for approximately 40% of the total care provided, with the balance being purchased from civilian providers. All the administrative events generated by either a direct care or purchased care inpatient or outpatient encounter are centrally processed into the MDR. Examples of the data recorded in such encounters include patient demographic data, provider information (provider ID, specialty, facility), diagnostic codes (ICD-9 codes for outpatient; diagnosis-related group [DRG] codes for inpatient), and Current Procedural Terminology (CPT) codes for any procedures. Extensive information regarding the patient, including age, race, and gender, is also stored within the MDR via connections with the Defense Eligibility Enrollment Reporting System (DEERS). The military utilizes an electronic medication system called the Pharmacy Data Transaction System (PDTS). All the prescribing details of both direct care and purchased care outpatient medication orders, including mail order, are electronically coded, including the prescribed drug name and NDC, dose, quantity, refills, and prescribing provider. All PDTS information is fed into the MDR.

In addition to feeding data into the MDR, direct care encounters conducted at MTFs utilize the military's EMR system, called AHLTA. This robust EMR system stores the entire encounter electronically and is powered by the MEDCIN® Engine; AHLTA is therefore designed with extensive variables documenting the individual components of an encounter, including symptoms, vital signs, history, physical exams, laboratory and radiology results, diagnostic codes, procedure codes, pharmacy orders, and other orders such as specialty consultation. The AHLTA dataset for each encounter is stored within the Clinical Data Repository (CDR). Aspects of the CDR feed into the MDR, including vitals and lab results. Administrative information such as ICD-9 diagnoses, CPT codes, and pharmacy orders for all direct care encounters are held in common by the CDR and MDR. The CDR is a transactional database required to provide millions of interactions every day for hundreds of thousands of users.

[figure not shown]

Figure 1

Age distribution among DOD active patients

9.5 STUDY SIZE

Given the non-interventional design, the study's objective is not to demonstrate superiority of dabigatran vs. rivaroxaban or apixaban but rather to provide real-world estimates of the comparative effectiveness and safety of dabigatran, rivaroxaban, and apixaban in a large US population of NVAF patients. Therefore, the planned analyses are descriptive in nature and results of the statistical tests are to be interpreted in an exploratory manner.

For each treatment comparison, the available sample size is determined by feasibility assessments of the DoD database according to the pre-specified time window and inclusion/exclusion criteria, and not by formal sample size justifications. Therefore, the purpose of the power assessments described in this section is to illustrate the precision of the effect estimates that can be achieved given the feasible sample size. The primary safety outcome of major bleeding was used for the power assessments, for which an annual event rate of 3.1% for the dabigatran patients and a mean follow-up duration of 0.82 years for both groups were assumed based on the study by Villines et al⁶. In addition, all calculations are based on a two-sided test with $\alpha=0.05$ and a 10% loss of dabigatran patients during the 1:1 propensity score matching.

For the analysis of dabigatran vs. rivaroxaban, it is estimated that a total of approximately 41,000 patients (16,000 dabigatran vs. 25,000 rivaroxaban patients) will be available for this study, based on the proposed time window of July 2011 to March 2016. Power calculations suggest that such a sample size will allow the study to detect a relative difference in the rate of major bleeding of 22% with 80% power, and 25% with 90% power, between the rivaroxaban and dabigatran groups.

For the analysis of dabigatran vs. apixaban, it is estimated that a total of approximately 27,000 patients (6,000 dabigatran and 21,000 apixaban patients) will be available for this study, based on the proposed time window of December 2012 to March 2016. Power calculations suggest that such a sample size will allow the study to detect a relative difference in the rate of major bleeding of 37% with 80% power, and 43% with 90% power, between the apixaban and dabigatran groups. The analysis may therefore have insufficient power to detect a smaller treatment difference if the expected sample size is confirmed.

The actual power of the study will be dependent on the actual event rate in each treatment group, the covariates included in the analysis models, and the actual loss of patients during matching, and may therefore differ.

9.6 DATA MANAGEMENT

Access to the DoD data will be through a VPN connection. Through this secure connection [REDACTED] and [REDACTED] will construct the study-specific analytic datasets. Data are checked for internal consistency within each patient's claims/records relevant to the study analyses and any patients with extreme or unexpected treatment patterns or diagnoses are identified. BIPI will not have direct access to the raw data. All data management and statistical analyses will be performed using SAS Version 9.4 (or later) in the secured environment

9.7 DATA ANALYSIS

All statistical analyses will be performed using SAS version 9.4 (SAS Institute, Cary, NC).

Baseline characteristics will be described for the two cohorts based on the NOAC treatment (dabigatran vs. rivaroxaban and dabigatran vs. apixaban) using standard summary statistics. Means (\pm standard deviation, SD) and median (interquartile range) will be reported for continuous variables and frequencies (%) for categorical variables. The final study sample will be newly initiating cohorts.

To account for potential selection bias, the study cohorts (dabigatran/rivaroxaban and dabigatran/apixaban) will be matched on their baseline characteristics using the propensity score matching (PSM) method. The PSM aims to balance the two treatment groups on baseline demographics, health plan type and clinical characteristics. The feasibility of PSM will be evaluated based on available sample size and descriptive results. If patient characteristics between dabigatran/rivaroxaban and dabigatran/apixaban cohorts are significantly different, i.e., less than 50% of patients in the dabigatran group can be matched to the rivaroxaban or apixaban group based on PSM, then the study design will be re-evaluated before proceeding to analysis. The Nearest Neighbor method of propensity score matching within a caliper of 0.10-0.20 (depending on resulting sample sizes) of the standard deviation of the estimated logit will be used to select the matched samples.

The propensity score will be defined as the probability of being treated with the index NOAC based on a set of baseline characteristics. If, for example, two patients, one in the dabigatran group and another in the rivaroxaban group, had the same propensity score, they would both have the same probability of being treated with dabigatran. The final list of baseline characteristics to be utilized in the PSM will be decided in conjunction with BI. The following baseline characteristics in the pre-index period will be considered: age, gender, health plan type, geographic region, month and year of index date, Charlson comorbidity index (CCI), stroke risk scores (i.e. CHADS₂ or CHA₂DS₂-VASc), bleeding risk scores (i.e., modified HAS-BLED), relevant baseline comorbid conditions and medication use as defined in Section 9.3.3. The distribution of baseline characteristics will be presented before and after the matching process. For baseline covariates that are not sufficiently balanced after PSM, the covariates will be included in an appropriate multivariate model to adjust for those differences.

9.7.1 Main analysis

Patient demographics and clinical characteristics will be reported for NVAF patients by treatment groups: dabigatran, rivaroxaban, or apixaban. Stroke risk will be quantified using the CHADS₂ score, CHA₂DS₂-VASc score and bleeding risk through the HAS-BLED score. In addition, administrative variables of eligibility time and post-index follow-up time will be described. Other descriptive variables may include, but are not limited to, the following:

Comorbid conditions at baseline (the 12 month pre-index period), based on diagnosis codes:

- Cancer
- Rheumatoid arthritis
- Coronary artery disease
- Acute myocardial infarction
- Cardiomyopathy
- Ischemic stroke
- Stroke (all types)
- TIA
- Congestive heart failure
- Left ventricular heart failure
- Hypertension
- Peripheral artery disease
- Liver disease
- Renal disease
- COPD/emphysema
- Diabetes
- Peptic ulcer (bleeding or non-bleeding)
- GERD
- Venous thromboembolism
- Hyperlipidemia
- HIV infection

- Bone marrow disease (thrombocytopenia, chronic anemia, myelofibrosis)
- Coagulopathy (hemophilia, Von Willebrand disease)
- Chronic kidney disease

Medication History and Concomitant Use at baseline (the 12 month pre-index period), based on prescription information:

- **Non-Oral Anticoagulants:** Number of prescription fills (normalized to a 30-day supply) will be captured during the pre-index period (See [Appendix A, Table 8](#))
 - Argatroban (can be used in procedures in lieu of heparin)
 - Unfractionated Heparin (Heparin)
 - Low Molecular Weight Heparins:
 - Enoxaparin
 - Tinzaparin
 - Dalteparin
 - Fondaparinux
- **Other medication use:** Use of other medications will be determined if patients had ever filled a medication in the following drug classes during the pre-index period (See [Appendix A, Table 3, Table 8](#)).
 - Beta blockers
 - Calcium channel blockers
 - Diuretics
 - Other antihypertensives (i.e., angiotensin-converting-enzyme (ACE) inhibitors, combinations)
 - Antihyperlipidemics
 - Corticosteroids
 - Antidiabetics
 - Antiarrhythmics (Amiodarone HCl, Propafenone and Flecainide, Dronedarone, Betapace (Sotalol), Tikosyn, Disopyramide (Norpace), Quinidine)
 - Ketoconazole
 - Antiplatelets (e.g., dypridamole, aspirin, etc.)
 - NSAIDs

The follow-up period, which comprises the patient-time denominator, will start at index and will be censored at the first occurrence of either of the following:

- outcome event
- therapeutic switch
- index NOAC dose change
- discontinuation of therapy, as defined as a gap in therapy exceeding 30 days
- end of DOD eligibility
- end of study period

[figure not shown]
Patients need at least two days of exposure to the index NOAC to ensure they had at least one day of index NOAC exposure in the post-index follow-up period.

For patients, index exposure will be considered discontinued if there is a treatment gap longer than the 30 day allowable gap specified from the end of the calculated days supplied.

Patients that have treatment gap longer than the specified allowable gap will be censored at that point and follow-up will be discontinued. A sensitivity analysis will be performed on patients that have treatment gaps longer than 14 days to determine if an adjustment to the gap days is necessary.

The first occurrence of each outcome will be identified, separately. For each outcome, event rates and 95% confidence intervals (CI) will be calculated using a person-time approach for each treatment and further stratified by age and gender. To compare the occurrence of each outcome between treatments, Kaplan-Meier analysis and Cox proportional hazards model analysis will be performed. Additional adjustments will be made for baseline variables that are not sufficiently balanced after PSM.

Standard dosing for each NOAC will be used for main analyses. All doses for each NOAC will be combined for a sensitivity analysis as defined below.

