Data analysis:	
The target population will include OAC treatment naïve NVAF patients with at least one prescription claim for dabigatran, rivaroxaban or apixaban. For each patient treated with a NOAC, the date of the first NOAC prescription (index exposure) will serve as the index date. Only those patients whose index date occurs between the respective study periods will be included. The 12-month period prior to the index date will be defined as the pre-index period. The patients will be required to have a NVAF diagnosis in the pre-index period (including index date).
 
Study period NOT including pre-index period:
 
 • Dabigatran vs. Rivaroxaban: July 1, 2011 to June 30, 2016 • Dabigatran vs. Apixaban: December 28, 2012 to June 30, 2016 
Study period including pre-index period:
 
 • Dabigatran vs. Rivaroxaban: July 1, 2010 to June 30, 2016 • Dabigatran vs. Apixaban: December 28, 2011 to June 30, 2016 
Standard dosing for each NOAC will be used for main analyses. All doses for each NOAC will be combined for a sensitivity analysis. Standard dose for NOAC's:
 
 • Dabigatran 150 mg, twice daily, total daily dose of 300 mg • Rivaroxaban 20 mg, once daily, total daily dose of 20 mg • Apixaban 5 mg, twice daily, total daily dose of 10 mg 
Length of Follow-up:
 
The post-index follow-up period will begin the day following the NOAC index date and end on whichever of the following occurs earliest:
 
 • The day of discontinuation of the index NOAC exposure; • The day before a switch to an anticoagulant different from the index exposure; • The day before a change in dose for the index NOAC; • The end of continuous eligibility of a patient in the health plan (disenrollment); • The end of the study observation period; or • The date of death of the patient. • The last date of calculated days supplied if treatment gap

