
>30 days
 
Patients need at least two days of exposure to the index NOAC to ensure they had at least one day of index NOAC exposure in the post-index follow-up period. A sensitivity analysis will also be performed using a 14 day treatment gap.
 
Both claims-level data, including diagnosis codes, procedure codes, pharmacy dispensed drugs, cost information, and enrolment data, as well as EHR-level data, including relevant lab tests and results, will be extracted for all applicable patients. Patient demographics, treatment history, and comorbidities, will be derived from the electronic database. Start and stop dates of each course of treatment will be coded from the pharmacy and medical claims data using rules to be developed in the study protocol. Comorbidities of interest will be ascertained through ICD-9 and ICD-10 diagnosis codes, in combination with procedures and medications, as appropriate to the study protocol definitions.
 
To account for potential selection bias, the study cohorts (dabigatran/rivaroxaban and dabigatran/apixaban) will be matched on their baseline characteristics using the propensity score matching (PSM) method. The PSM aims to balance the two treatment groups on baseline demographics, health plan type and clinical characteristics. The feasibility of PSM will be evaluated based on available sample size and descriptive results. If patient characteristics between dabigatran/rivaroxaban and dabigatran/apixaban cohorts are significantly different, i.e., less than 50% of patients in the dabigatran group can be matched to the rivaroxaban or apixaban group based on PSM, then the study design will be re-evaluated before proceeding to analysis. The Nearest Neighbor method of propensity score matching within a caliper of 0.10-0.20 (depending on resulting sample sizes) of the standard deviation of the estimated logit will be used to select the matched samples.
 
The propensity score models will include baseline variables known to be confounders or factors related to the outcome only, including age, gender, health plan type, geographic region, month and year of index date, Charlson comorbidity index (CCI), stroke risk scores (i.e. CHADS₂ or CHA₂DS₂-VASc), bleeding risk scores (i.e., modified HAS-BLED), specified comorbid conditions and medication use, based on literature and clinical relevance, as well as empirical data (top diagnoses, procedures, etc.) that may account for possible unforeseen confounding.

--

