Descriptive Statistics

Patient characteristics, including demographics, will be reported for NVAF patients treated with dabigatran, rivaroxaban, or apixaban. Stroke risk will be quantified using the CHADS₂, CHA₂DS₂-VASc score and bleeding risk through the HAS-BLED score. Other descriptive variables may include the following:

Comorbid conditions at baseline:

- Cancer
- Rheumatoid arthritis
- Coronary artery disease
- Acute myocardial infarction
- Cardiomyopathy
- Ischemic stroke
- Stroke (all types)
- TIA
- Congestive heart failure
- Left ventricular heart failure
- Hypertension
- Peripheral artery disease
- Liver disease
- Renal disease
- COPD/emphysema
- Diabetes
- Peptic ulcer (bleeding or non-bleeding)
- GERD
- Venous thromboembolism
- Hyperlipidemia
- HIV infection
- Bone marrow disease (thrombocytopenia, chronic anemia, myelofibrosis)
- Coagulopathy (hemophilia, Von Willebrand disease)
- Chronic kidney disease

Medication History and Concomitant Use:

- **Non-Oral Anticoagulants:** Number of prescription fills (normalized to a 30-day supply) will be captured during the pre-index period (See [Appendix A, Table 8](#))
 - Argatroban (can be used in procedures in lieu of heparin)
 - Unfractionated Heparin (Heparin)
 - Low Molecular Weight Heparins:
 - Enoxaparin
 - Tinzaparin

	
▪ Dalteparin▪ Fondaparinux• Other medication use: Use of other medications will be determined if patients had ever filled a medication in the following drug classes during the pre-index period (See Appendix A, Table 3, Table 8).
○ Beta blockers○ Calcium channel blockers○ Diuretics○ Other antihypertensives (i.e., angiotensin-converting-enzyme (ACE) inhibitors, combinations)○ Antihyperlipidemics○ Corticosteroids○ Antidiabetics○ Antiarrhythmics (Amiodarone HCl, Propafenone and Flecainide, Dronedarone, Betapace (Sotalol), Tikosyn, Disopyramide (Norpace), Quinidine)○ Ketoconazole○ Antiplatelets (e.g., dypiridamole, aspirin, etc.)○ NSAIDs
--	--

Outcome Analysis

The follow-up period, which comprises the patient-time denominator, will start at index and will be censored at the first occurrence of either of the following:

- outcome event
- switch to another anticoagulant
- change in dose of index NOAC
- discontinuation of therapy, as defined as a gap in therapy exceeding 30 days (a 14 day gap sensitivity analysis will also be performed)
- end of DoD eligibility
- end of study period

Primary outcomes

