6. MILESTONES

Milestone:	Planned date:
Protocol finalization	02 December 2016
BI Approval	05 December 2016
Start of data evaluation and specific programming rules development:	19 October 2016
Start of data analysis:	05 December 2016
Completion of ACC data analyses- Primary analyses with PSM	17 January 2016
Completion of data analyses- Secondary analyses with PSM	31 January 2017
Completion of data analyses- Sensitivity analyses (not including IPTW) with PSM	14 February 2017
Completion of data analyses- IPTW analyses	10 March 2017
Final report of study results:	March 2017

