- Valvuloplasty, tricuspid valve; with ring insertion
- Replacement, tricuspid valve, with cardiopulmonary bypass

Standard dosing for each NOAC will be used for main analyses. All doses for each NOAC will be combined for a sensitivity analysis. Standard dose for NOAC's include:

- Dabigatran 150 mg, twice daily for total daily dose of 300 mg
- Rivaroxaban 20 mg, once daily for total daily dose of 20 mg
- Apixaban 5 mg, twice daily for total daily dose of 10 mg

Length of Baseline

The 12-month period prior to and including the NOAC index date will be defined as the baseline period. Patients will be required to have an NVAF diagnosis during this baseline period.

The pre-index period will serve as a look-back period to measure baseline covariate data and apply other inclusion and exclusion criteria.

Length of Follow-up:

The post-index follow-up period will begin the day following the NOAC index date and end on whichever of the following occurs earliest:

- The day of discontinuation of the index NOAC exposure;
- The day before a switch to an anticoagulant different from the index exposure;
- The day before a change in dose for the index NOAC;
- The end of continuous eligibility of a patient in the health plan (disenrollment);
- The end of the study observation period; or
- The date of death of the patient.

Patients need at least two days of exposure to the index NOAC to ensure they had at least one day of index NOAC exposure in the post-index follow-up period.

For patients, index exposure will be considered discontinued if there is a treatment gap longer than the 30 day allowable gap specified from the end of the calculated days supplied.

Patients that have treatment gap longer than the specified allowable gap will be censored at that point and follow-up will be discontinued. A sensitivity analysis will also be performed using a 14 day treatment gap.

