9.8 QUALITY CONTROL

All amendments to the study protocol will be discussed with and agreed upon by the sponsor. Actual amendments to the study protocol will be made by the vendor and sent to BIPI for review and approval. The date of the amendments will be documented on the cover page of the study protocol. Amendments to the protocol will be submitted to the Institutional Review Board (IRB) for review and approval prior to implementation in accordance with regulatory requirements.

Clinicians from two MTFs, who are well versed in the standard of care for the NVAF population in the military setting, will be available to provide oversight and feedback.

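### Section 9.7.1 lets the 14-day gap analysis decide whether the 30-day rule is adjusted, with no visible criterion and after the main results are due

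*Combined protocol and SAP*

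**What the plan says.** **Main rule.** Sections 4, 9.2 and 9.7.1 all treat a gap of more than 30 days after the calculated days supplied as discontinuation, at which follow-up is censored.

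**Role of the 14-day run.** Section 9.7.1 says it will be "performed on patients that have treatment gaps longer than 14 days to determine if an adjustment to the gap days is necessary". The Abstract, under Data analysis, says only "A sensitivity analysis will also be performed using a 14 day treatment gap", and 9.2 repeats this. The Abstract's outcome analysis says "a 14 day gap sensitivity analysis will also be performed". None of these three places gives the run a deciding role.

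**Changing definitions.** Just before its list of potential analyses, the Abstract says that sensitivity, subgroup or exploratory analyses may lead to changes in how cohort, covariates or outcome are defined.

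**Timing.** Section 6 has a line "Completion of data analyses- Sensitivity analyses (not including IPTW) with PSM", dated 14 February 2017. The secondary analyses are due on 31 January 2017 and the primary ones on 17 January. The year of the latter is printed as 2016 but must be 2017, since analysis starts on 5 December 2016.

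**What cannot be seen.** Section 9.7.1 ends with "All doses for each NOAC will be combined for a sensitivity analysis as defined below", and nothing visible follows. The table of contents has a redacted entry between 9.7.1 and 9.8.

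**Change control.** Section 9.8 says "Amendments to the protocol will be submitted to the Institutional Review Board (IRB) for review and approval prior to implementation".

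**The concern.** A sensitivity analysis shows how far a result depends on a definition. Section 9.7.1 has it run the other way: the result informs whether the definition stays. If that decision is made with the dabigatran comparisons in view, the choice of gap can favour one arm, and the 95% confidence intervals will not reflect that a choice was made.

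The wording also leaves the analysis set unclear. Restricting the run to patients with gaps over 14 days conditions on refill behaviour after index. That behaviour may differ between drugs and may be related to bleeding or stroke, so such a subgroup loses the balance that matching was meant to give. A re-run of the whole matched cohort under a 14-day rule does not have this problem. Two programmers could build different analyses from the two descriptions.

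**Working it through.** **1. The plan's own figures.** Section 9.5 gives a 3.1% annual major bleeding rate on dabigatran, 0.82 years of mean follow-up, a 10% matching loss, 1:1 matching and two-sided alpha of 0.05. I take risk = 1 − exp(−rate × 0.82), a comparator rate of 3.1% × (1 + d), and the Schoenfeld formula.

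| Comparator | Pairs | d | Stated power | Recomputed |
|---|---|---|---|---|
| Rivaroxaban | 16,000 × 0.9 = 14,400 | 22% | 80% | 80.4% |
| Rivaroxaban | 14,400 | 25% | 90% | 88.9% |
| Apixaban | 6,000 × 0.9 = 5,400 | 37% | 80% | 80.4% |
| Apixaban | 5,400 | 43% | 90% | 90.0% |

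These reproduce and are not in dispute. Nothing below changes them.

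**2. Passages side by side.**

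| Place | 14-day run | Who is analysed | Consequence |
|---|---|---|---|
| 4, Data analysis; 9.2 | Re-run with a 14-day gap | Not restricted | None stated |
| 4, Outcome analysis | 14-day gap sensitivity analysis | Not restricted | None stated |
| 9.7.1 | Run to see if gap days need adjusting | Patients with gaps over 14 days | Possible change to the gap rule; no visible criterion |

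By completion date, the sensitivity analyses come 28 days after the primary analyses (17 January to 14 February) and 14 days after the secondary ones.

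**3. Illustration of size (assumptions mine).** Moving from 30 to 14 days removes follow-up after a first gap of 15 to 30 days. Let r be the share of person-time removed and k the event rate in removed time relative to kept time. Share of events kept = (1 − r)/(1 − r + rk).

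- r = 0.1, k = 0.5: 0.90/0.95 = 94.7%
- r = 0.2, k = 1.5: 0.80/1.10 = 72.7%

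The two test statistics are nested, so their correlation is about the square root of the share kept: 0.973 and 0.853. Under no difference, the chance that at least one of two such statistics exceeds 1.96 in absolute value is 6.1% and 7.4%, against 5% for one fixed rule.

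Expected major bleeds per arm, at the dabigatran rate in both arms:

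- Rivaroxaban comparison: 14,400 × 0.82 × 0.031 = 366 under 30 days; 347 to 266 under 14 days.
- Apixaban comparison: 5,400 × 0.82 × 0.031 = 137 under 30 days; 130 to 100 under 14 days.

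The rate ratio moves only if removal differs by arm and the removed time has a different rate. With r = 0.2 in one arm and 0.1 in the other, a rate ratio of 1.00 under 30 days becomes 0.95/0.90 = 1.06 (k = 0.5), 1.00 (k = 1) or 1.05/1.10 = 0.95 (k = 1.5).

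**4. Follow-up boundaries.** Mean follow-up is 0.82 × 365.25 = 299.5 days.

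- *Start:* the day after index (Length of Follow-up in 4 and 9.2) or at index (outcome analysis in 4, and 9.7.1). This is a direct conflict, worth 1/299.5 = 0.33%.
- *End at a gap:* the Abstract gives "The last date of calculated days supplied if treatment gap" exceeds 30 days. Section 9.2 says "Patients that have treatment gap longer than the specified allowable gap will be censored at that point and follow-up will be discontinued", and 9.7.1 repeats this; neither gives a date. The last day supplied and the end of the 30-day gap differ by 30 days, or 30/299.5 = 10.0% of mean follow-up for a patient censored this way.
- *Switch and dose change:* the day before, in the Length of Follow-up lists; named without a day rule in the outcome analysis of 4 and in 9.7.1. Section 9.3.2 omits dose change.
- *Death:* in the Length of Follow-up lists, but not in the other two censoring lists.

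**The case against.** The strongest reply is that a criterion may exist where it cannot be seen. The contents page shows a redacted entry right after 9.7.1, and that section points to text below that is not visible. This stands. A reader might infer that the sponsor set no rule; the documents support only that none is visible. The fix has to be conditional for that reason.

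Second, 30 days is stated firmly in several places, and the trouble comes from one clause. A reader might infer that the plan intends to swap the main estimate or to report whichever rule gives significance. No passage says so, and the 6.1% to 7.4% figure describes that behaviour only as a bound. But the clause is more than loose phrasing, because the Abstract separately contemplates sensitivity analyses changing definitions.

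Third, the Milestones give completion dates only, and programming rules were being developed from 19 October 2016. Gap patterns could be examined earlier, without outcomes. That is possible, but nothing visible requires it. Amendment and IRB approval would document a change without making it blind to results.

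Fourth, the boundary differences are mostly silences. This is largely right. In particular, a reader might take 9.3.2 to count events on the day of a switch. It says only that assessment does not go beyond that date, which is compatible with stopping the day before.

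**Conclusion.** The point holds as a clarification that should be made before analysis. Section 9.7.1 conflicts with the Abstract and 9.2 on what the 14-day run is for and on whom it is performed, and it leaves the main gap definition open to change after comparative results are seen.

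The consequence is modest. Section 9.5 calls the analyses descriptive and the tests exploratory, so the issue is which estimate counts as the main one rather than formal error control. The true size cannot be computed. The illustration rests on assumed values (10% to 20% of person-time removed, with 0.5 to 1.5 times the event rate) and on an analyst taking the more favourable result. With equal removal in both arms, or equal rates in removed and kept time, the rate ratio does not move at all.

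The boundary points are minor. The start date is a true conflict but trivial in size. The gap end date is left undefined in 9.2 and 9.7.1 and deserves one line. Confidence is medium because of the redaction.

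**What to change.** 1. **Section 9.7.1.** Replace the 14-day sentence with: *The 30-day gap is the primary definition whatever the 14-day result shows; the 14-day gap rule is applied to the full matched cohort and reported alongside.* If redacted text already holds a rule fixed before outcomes are seen, cite that rule instead.
2. **Abstract.** Amend the statement that sensitivity analyses may change definitions, so that their results are reported alongside and leave the primary definitions unchanged. Without this, item 1 does not close the issue.
3. **Sections 4, 9.2, 9.3.2 and 9.7.1.** Use one set of follow-up boundaries. State a single start; the day after index fits the existing two-day exposure requirement. Carry the Abstract's end date for a gap (last day supplied) into 9.2 and 9.7.1, or reconcile all three to another single date. State one boundary for switch and dose change, and include death in every censoring list.

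The cost is protocol wording. No sample size or power figure changes. The sponsor gives up only the option of changing the main gap rule after seeing results.
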